Muscle strength and power deficits are significant post-stroke: Figure 2 illustrates deficits in the ability to generate peak torque in the plantar flexor and knee extensor muscle groups in a group of subjects post-stroke ($n=7$ with moderate to severe motor impairments), relative to matched (gender, age, height and weight) neurologically healthy individuals. Specifically, peak torque production in the paretic and non-paretic muscles was 76% and 62% lower in the plantar flexors and 78% and 61% lower in the knee extensor muscle group, respectively. In addition, the average rate of torque development (ARTD), defined as the time integral necessary to generate from 20 to 80% of peak torque, was significantly reduced in person's post-stroke (~89% and 78% in paretic and non-paretic muscle, respectively), indicative of substantial deficits in muscle power generation in these muscle groups. Deficits in torque production in our subjects were associated with reduced voluntary activation in both the knee extensor and plantar flexor muscle groups (Figure 2). Central activation impairment is only ~5% in neurologically healthy individuals, whereas paretic central activation impairments are 66% and 64%; and non-paretic activation impairments are 40% and 52%; in the KE and PF muscle groups, respectively. Collectively, our data demonstrate significant muscle force generation dysfunction in both paretic and non-paretic limbs that is partially explained by reduced central activation of these muscles following stroke.

[figure not shown]

Figure 2: Peak torque and voluntary activation deficits in paretic (black bars), non-paretic (white bars) and control (grey bars) PF and KE muscle groups

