In addition to improved walking speeds, peak muscle power generation during strength testing increased in the paretic and non-paretic plantar flexor (64.9% and 52.5%; Figure 12) and knee extensor (62.3% and 68.7%) muscles. Contributing to increases in muscle power, peak torque production increased in paretic and non-paretic plantar flexor (39.7% and 47.7%) and knee extensor (23.3% and 32.6%) muscle groups. In addition, greater plantar flexor peak velocity of contraction in paretic (154 ± 39 $^{\circ}$ sec $^{-1}$ pre vs. 237 ± 55 $^{\circ}$ sec $^{-1}$ post) and non-paretic (213 ± 44 $^{\circ}$ sec $^{-1}$ pre; 306 ± 69 $^{\circ}$ sec $^{-1}$ post) legs as well as increases in paretic (12.8%) and non-paretic (9.1%) cross-sectional area also resulted from training. Similarly, increases in peak contractile velocity as well as muscle CSA and voluntary activation for the KE muscle group also resulted from training.

[figure not shown]

Figure 12: Individual subject peak paretic plantar flexor muscle power generation during dynamometric evaluation (A) as well as during self-selected walking speed (B) at pre (black bars) and post (red bars) POWER training time points.

D. RESEARCH DESIGN AND METHODS (including data analysis)

Procedures Relative to Specific Aims:

Aim 1: Determine the presence and magnitude of neural and muscular adaptations as

predictors of impaired muscle power generation in persons post-stroke.

Rationale: Our preliminary data indicate a significant reduction in peak torque generation in the plantar flexor and knee extensor muscle groups relative to matched (gender, age, height and weight) controls. In addition, reductions in muscle cross-sectional area (CSA) along with impaired central activation and altered *in-vivo* bioenergetic properties (e.g., increased [Pi]) are also characteristic of muscle post-stroke and likely contribute significantly to hemiparetic muscle dysfunction. To date, the physiological mechanisms that contribute to hemiparetic muscle dysfunction are largely unstudied.

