Summary of Experiment & Research Design: We will perform comprehensive dynamometric, electrophysiological and magnetic resonance assessments of paretic and non-paretic musculature. Measurements will be performed on a total of 28 subjects at least six months following stroke and comparisons made to the dominant leg of a group of matched (age, gender, height & weight) neurologically healthy individuals (n=28). In doing so, we will determine if, and to what extent, neural and muscular factors differ between legs (paretic vs. non-paretic vs. control). In addition, we will determine the relationship between these factors and impaired muscle power generation. Our primary outcome measures in the ankle plantar flexor and knee extensor muscle groups will include 1) peak torque and power generation determined via isokinetic and isotonic dynamometry, respectively; 2) central activation measured using superimposed neuromuscular electrical stimulation; 3) muscle cross-sectional area (CSA) determined via MRI; and 4) muscle oxidative capacity (reflected by the rate of PCr recovery) and resting concentrations of inorganic phosphate [Pi] measured using ^{31}P MR spectroscopy.

Data Analysis Plan: The influence of neural and muscular adaptations (central activation, muscle CSA, *in-vivo* oxidative capacity and [Pi]) on peak power generation at baseline will be conducted using mixed effect regression models. The mixed models will be used with random subject effects to account for the dependent nature of the data collected on paretic and non-paretic legs within the same individuals. The baseline measure of peak power generation will serve as the dependent variable, with fixed effects for leg involvement (paretic vs. non-paretic) and for neural and muscular adaptation measures. Model fit will be assessed via Akaike Information Criteria (AIC). Partial correlations and standardized β coefficients will determine those factors with the strongest influence on muscle power generation. The models will also allow us to address secondary questions such as the differences between peak power generation and neural and muscular adaptation measures in paretic and non-paretic limbs.

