Expectation: We hypothesize that the strongest predictor of impaired muscle power generation in the paretic and non-paretic legs will be central activation. Further, *in-vivo* oxidative capacity and [Pi] in both the paretic and non-paretic legs will be weakly associated with peak power generation, while CSA will only be significant in the paretic leg. We also expect significant reductions in paretic peak power generation, central activation, CSA and *in-vivo* oxidative capacity as well as an increase in [Pi], when compared to non-paretic and control legs. Further, differences in peak power, central activation and [Pi], but not CSA, will be present between the non-paretic and control legs.

Innovation: The proposed investigation combines contemporary, high resolution MR imaging and spectroscopic techniques concurrently with electrophysiological assessment of central activation impairment and dynamometric evaluations of muscle strength and power, which together will produce unequivocal evidence of the presence, magnitude and relative importance of neural and muscular factors as contributors to impaired hemiparetic muscle function.

Aim 2: Quantify the effects of POWER training on the presence and magnitude of neural and muscular adaptations in paretic and non-paretic muscle post-stroke

Rationale: To date, the physiological mechanisms that contribute to improvements in lower extremity muscle power generation in hemiparetic subjects are largely unstudied. Moreover, how these variables impact functional performance would provide a foundation for the development of effective rehabilitation interventions targeting functional recovery post-stroke.

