Sample size determination and Statistical Approach: A total of 28 subjects will be recruited for this study. With baseline data from n=28 subjects, we will have at least 80% power to detect measures of association (i.e. partial correlations) as small as 0.5 between neural/muscular adaptations and peak power generation. Our preliminary data suggest that the intraclass correlation between measures of power on paretic and non-paretic legs is extremely high (i.e. Spearman rho = 0.81, intraclass correlation coefficient [ICC - from mixed model] ~100%). This power estimate for Aim 1 is based on 1 observation per subject; although our mixed model approach for analyses for Aim 1 will include 2 observations per subject (i.e. paretic and non-paretic leg), the detectable correlation may not be substantially lower due to the strong intraclass correlation. For Aims 2 and 3, analyses rely on longitudinal measures, and we assume (based on experience with our patient population) that no more than 15% will fail to complete all assessments. With 28 subjects enrolled and a 15% attrition rate over time (resulting in complete data on 24 subjects), we would have at least 80% power to detect changes in measures from baseline to the end of the study equivalent to 0.6 standard deviation units (i.e. effect sizes). This power estimate is based on a paired t-test framework (i.e. pre-post comparisons), and thus power is likely underestimated, since our models will also include data from mid-intervention and follow-up time periods. For example, assuming an ICC of 90% associated with within-subject responses over 4 time periods, the effective sample size (see Campbell et al., 2001) would be slightly higher (~n=26), as would be our power (~83%) to detect an effect size of 0.6. Treatment effect sizes of 0.6 are consistent with our preliminary data, in which effect sizes of 0.7 (95% CI 0.5 to 0.9), 1.5 (95% CI 1.1 to 1.9, and 0.5 (95% CI 0.1 to 1.0) were observed for improvement in gait speed, paretic leg power, and non-paretic power, respectively. With complete data on 24 subjects, we will also be able to detect whether as little as 40% of the variability in changes in gait speed can be explained by changes in the neural / muscular adaptation measures, assuming an ICC of 90% associated with within-subject responses over 4 time periods. All power estimates assume 2-sided hypothesis tests and an alpha level of 0.05 and were conducted by a biostatistician using PASS 2008 (NCSS, Kaysville, Utah).

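### Aim 1 takes the paretic versus non-paretic contrast from a model that adjusts for the presumed causes of the deficit, so its leg coefficient understates the total power deficit and gives no leg difference for the adaptation measures

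*Combined protocol and SAP*

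**What the plan says.** All references are to the combined protocol and SAP.

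- **Section D, Aim 1, Data Analysis Plan.** One model form is described, a mixed model with a random subject effect. Its outcome is baseline peak power, and the predictors are entered "with fixed effects for leg involvement (paretic vs. non-paretic) and for neural and muscular adaptation measures". The adaptation measures listed are central activation, CSA, oxidative capacity and [Pi]. The same paragraph adds that the models will also "address secondary questions such as the differences between peak power generation and neural and muscular adaptation measures in paretic and non-paretic limbs".
- **Section D, Aim 1, Expectation.** The hypothesis on the legs begins "We also expect significant reductions in paretic peak power generation, central activation, CSA" and goes on to lower oxidative capacity and higher [Pi], in comparison with both the non-paretic and the control legs. It also states that "the strongest predictor of impaired muscle power generation in the paretic and non-paretic legs will be central activation".
- **Section D, Aim 1, Rationale.** Reduced CSA, impaired activation and altered bioenergetics are said to "likely contribute significantly to hemiparetic muscle dysfunction".
- **Sample size determination and Statistical Approach.** Aim 1 is sized only for partial correlations ("With baseline data from n=28 subjects").

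No baseline model with leg as the only fixed effect appears anywhere. The analysis of leg differences under Aim 2 concerns change over time.

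**The concern.** The Expectation describes a total deficit: how much less power the paretic leg produces, whatever the reason. The stated model estimates something else, namely how much less power a paretic leg produces than a non-paretic leg with the same activation, size and bioenergetics. Those factors are the ones the plan believes lie between the stroke and the loss of power. Adjusting for them removes from the leg coefficient the share of the deficit that runs through them, and the more of the deficit they carry, the more is removed.

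The sentence also promises leg differences in the adaptation measures. A model in which they are predictors gives none.

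At stake is the descriptive half of Aim 1, which is whether and by how much the two legs of a patient differ. Read from the stated model, the power deficit would be reported as smaller than it is. The contrasts in activation, CSA, oxidative capacity and [Pi] would have no stated analysis. The control-leg contrasts hypothesised in the same paragraph are a separate matter.

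**Working it through.** **1. The plan's own figure.** The plan claims at least 80% power for a partial correlation of 0.5 with 28 subjects, two-sided alpha 0.05. Fisher's z gives Φ(atanh(0.5) × √(28 − 3) − 1.96) = Φ(0.549 × 5 − 1.96) = Φ(0.787) = 78.4%. A simulation of the exact bivariate-normal test gives 80.0%. The figure reproduces when no other covariate is partialled out. It sizes the predictor question and says nothing about the leg contrast.

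**2. Direction.** On a scale where effects add (for example log power), write g for the paretic minus non-paretic gap in a factor and b for its slope in the joint model. Then

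total leg difference = adjusted leg coefficient + Σ(b × g).

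For activation, CSA and oxidative capacity the plan expects g < 0, and its premises imply b > 0. For [Pi] it expects g > 0, with b < 0 implied. Every product is then negative, so the adjusted coefficient is less negative than the total. This step needs only the plan's premises.

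**3. Size, plantar flexors.** The inputs come from section C, Preliminary Studies:

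| Quantity | Paretic / non-paretic | Ratio | Sample |
|---|---|---|---|
| Peak torque (76% and 62% below control) | 0.24 / 0.38 | 0.632 | n=7 |
| Activation (64% and 52% impaired) | 0.36 / 0.48 | 0.750 | n=7 |
| CSA, soleus (20% and 13% smaller) | 0.80 / 0.87 | 0.920 | n=17 |
| CSA, lateral gastrocnemius (16% and 6%) | 0.84 / 0.94 | 0.894 | n=17 |
| CSA, medial gastrocnemius (27% and 9%) | 0.73 / 0.91 | 0.802 | n=17 |
| Peak contraction velocity before training, °/s | 154 / 213 | 0.723 | n=5 |

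The outcome is power, not torque, so I take the power ratio as torque ratio × velocity ratio = 0.632 × 0.723 = 0.46, a 54% deficit.

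Adjusted ratio = 0.457 / (activation ratio × CSA ratio)^b, where b is the assumed strength of the relation:

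- b = 1 (proportional): soleus 0.457 / (0.750 × 0.920) = 0.66; lateral gastrocnemius 0.457 / (0.750 × 0.894) = 0.68; medial gastrocnemius 0.457 / (0.750 × 0.802) = 0.76. The remaining deficit is 24–34%.
- b = 0.5 (square root): 0.457 / √0.690 = 0.55; 0.457 / √0.670 = 0.56; 0.457 / √0.602 = 0.59. The remaining deficit is 41–45%.
- b = 0: 0.46, unchanged.

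Oxidative capacity and [Pi] are left out of this arithmetic. I give no rejection rates: the preliminary data include no standard deviations for torque, activation or CSA by leg, and any rate would follow the values assumed.

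**The case against.** **The wording may not commit the authors to this model.** The text speaks of models in the plural and compares fit by AIC. The sentence promises leg differences in the adaptation measures, which no model with power as outcome can give, so separate models may be intended. It may also mean leg-specific associations, in line with the expectation that CSA matters only in the paretic leg. Both readings are possible, but neither is written down. The Aim 2 plan says explicitly that each adaptation is the outcome of its own model, and the Aim 1 plan does not. Leg-specific associations would need leg-by-factor interactions, which are not listed, and the hypothesised total deficit would still lack an analysis.

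**The plan does not expect these factors to explain everything.** This stands. Section B (Muscle power) says that mass and activation do not account for power falling more than strength. Section B (Central activation) says that activation does not fully explain the weakness. A remaining leg difference is therefore expected, and the theory does not imply a coefficient near zero.

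**A stronger reading is tempting: that the deficit could reverse.** From torque alone, the knee extensor ratio is 0.22/0.39 = 0.564. Dividing by activation (0.34/0.60 = 0.567) and CSA (0.76/0.95 = 0.80) gives 1.24, as if the paretic leg were stronger. The documents do not support carrying this over to power, which also depends on velocity. No knee extensor velocity by leg is given. If its ratio were like the plantar flexors' 0.72, the result would be 1.24 × 0.72 = 0.90. The crossing point is a velocity ratio of 1/1.244 = 0.80.

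**It is a secondary question.** This is true, and the primary predictor analysis rightly includes the adaptation measures. But the Aim 1 design summary sets out to establish whether and how far the factors differ between legs, so the contrast needs a correct analysis.

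**Conclusion.** The point holds for the secondary paretic versus non-paretic contrasts. As written, the leg coefficient is the part of the power difference that the measured factors do not explain. If those factors are worse in the paretic leg and related to power, as the plan holds, the coefficient understates the total deficit. The adaptation measures have no stated leg contrast.

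The direction rests on the plan's premises. The size does not. The plantar flexor shift from about 0.46 to 0.66–0.76 assumes power equals torque times velocity, output proportional to activation times CSA, and ratios combined from different pilot samples of 5, 7 and 17. With the square-root relation it is 0.55–0.59.

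A reader might infer that the paretic deficit would vanish or reverse, or that the main Aim 1 analysis is wrongly adjusted. The documents support neither. A reversal is not established for peak power, and the partial-correlation analysis is unaffected.

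**What to change.** Keep the adjusted model for the predictor question only. Replace the sentence on secondary questions with a stated analysis of the leg contrasts:

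- For each of peak power, central activation, CSA, oxidative capacity and [Pi], in each muscle group measured, fit a random-subject model with that measure as outcome and leg as the only fixed effect. Report the paretic minus non-paretic mean difference with a 95% CI.
- Where the leg coefficient of the adjusted model is reported, label it as the part of the deficit not explained by the measured factors.
- If leg-specific associations are also intended, say so and list the leg-by-factor interactions.

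The cost is a short change to the analysis text and a few simple models on data already collected. There are no new subjects or procedures, and the sample size does not change.

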Summary of Experiment & Research Design: Twenty-eight subjects will participate in a novel training paradigm targeting lower extremity muscle function. Training will take place over an 8-week period, three times per week on non-consecutive days. Exercises will be performed in the paretic and non-paretic limbs separately and progressed as tolerated across the 8-week period. Dynamometric evaluations of isokinetic strength and isotonic power will be performed prior to, after 4 and 8 weeks of training as well as 8 weeks following cessation of training (Figure 13). Assessments of muscle morphology (CSA) and in-vivo bioenergetics (PCr recovery and [Pi]) as well as full biomechanical assessments of walking will be performed at the same time points, allowing determination of the efficacy (and persistence) of training on the proposed outcomes. We will perform walking analysis over-ground and on the instrumented treadmill by collecting: (i) kinetics (3-dimensional ground reaction forces and moments), (ii) kinematics and iii) EMG from each leg. For each kinesiological measure, averages over the gait cycle for each leg will be calculated for each subject. Our primary outcome measures during biomechanical assessments will be peak ankle plantar flexion and knee extension power generation, with secondary variables of interest to include paretic step length ratio and paretic propulsion. A battery of clinical assessments to evaluate degree of function and disability will be performed prior to as well following training and at the 8 week post-training time point (see **Procedures-Specific**).

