Data Analysis Plan: To quantify the effects of our POWER training intervention on neural and muscular adaptations, we will utilize repeated measures mixed effects regression models to assess for significant changes in our outcomes over time. Neural and muscular adaptations (on both the paretic and non-paretic legs) will serve as dependent variables in separate models, with time serving as the key independent variable in each. Various error structures associated with the repeated measures over time will be considered (e.g. compound symmetry vs. auto-regressive), and final error structures will be selected based on AIC values. Having random subject effects in the models will account for correlation among measures within subjects over time. Secondary analyses, incorporating differences in the paretic and non-paretic legs as dependent variables, will examine whether changes over time are more pronounced in the paretic vs. non-paretic leg. These models will also incorporate random subject effects to account for within-subject dependence. Error correction will be set to maintain type one error at 5% with a desired power of 80%.

Expectation: We hypothesize that POWER training will result in significant increases in muscle peak power generation, central activation, muscle CSA and in-vivo oxidative capacity as well as a concomitant decrease in [Pi]. Further, we expect changes in these variables will be greater in the paretic compared to the non-paretic leg. We also expect improvements in Clinical Assessments as a result of training as well as increases in our measures of locomotor function (see **Procedures-Specific**).

Innovation: Through conduct of the proposed experiments, we will generate a rich data set, capable of relating measures of lower extremity power generation (both in and away from the task of walking) with functional walking performance. The proposed neuromuscular assessment

[figure not shown]

Figure 13: Timeline for measures during POWER training

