
E. PROTECTION OF HUMAN SUBJECTS

1. Risks to the subjects

a. Human Subjects Involvement and Characteristics: We will recruit twenty-eight subjects with persistent motoric disability following a single stroke or two strokes on the same side of the brain, the most recent no less than six months prior. Subjects may be between 50 and 70 years of age, of either sex, and of diverse ethnic background. Subjects who have experienced more than one stroke will be accepted only if all strokes are on the same side of the brain, there is no history of a clinical ischemic or hemorrhagic event affecting the other hemisphere, and there is no evidence of more than a lacune or minor ischemic demyelination affecting the other hemisphere. Subjects will be recruited to participate in 8-weeks of a high-velocity resistance training paradigm designed to target lower extremity power generation. We will perform comprehensive dynamometric and magnetic resonance assessments of the paretic and non-paretic hip, knee and ankle musculature. In addition, we will also perform analysis of over-ground walking on an instrumented treadmill. During walking we will collect: (i) kinetics (3-dimensional ground reaction forces and moments),

(ii) kinematics (3-D) and iii) EMG from each leg as well as self-selected and fastest comfortable walking velocities. We will also perform a battery of clinical assessments to evaluate degree of function and disability. In addition to our post-stroke participants, we will also recruit twenty-eight neurologically healthy controls matched on the basis of age, gender, height and weight. Control subjects will participate in dynamometric and magnetic resonance evaluations but will not complete the training.

Subjects (male and female), ages 50-70, will be screened and recruited for the study six months to two years post-stroke, allowing for natural recovery during the first 6 months post-stroke. The pool of candidates for the study will be recruited from rehabilitation programs at the Ralph H. Johnson VAMC; the Medical University of South Carolina; and Charleston area communities. Eligible participants will be screened for participation and if appropriate will be accepted into the study for training.

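### Aim 2 claims to determine the efficacy and persistence of training, but a single trained group analysed over time can show only within-patient change and its retention

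*Combined protocol and SAP*

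**What the plan says.** The Aim 2 design summary (section D) sets out dynamometry, magnetic resonance measures and walking biomechanics at four times: before training, after 4 and 8 weeks of it, and 8 weeks after it stops. It describes this schedule as "allowing determination of the efficacy (and persistence) of training on the proposed outcomes".

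The same summary gives the training part one arm: "Twenty-eight subjects will participate in a novel training paradigm targeting lower extremity muscle function". Both legs are treated: "Exercises will be performed in the paretic and non-paretic limbs separately and progressed as tolerated across the 8-week period". Section E.1a gives the role of the matched healthy group: "Control subjects will participate in dynamometric and magnetic resonance evaluations but will not complete the training".

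The Aim 2 Data Analysis Plan fits a separate repeated-measures mixed model for each outcome, "with time serving as the key independent variable in each". A secondary analysis compares change between the two legs. The sample-size section claims "at least 80% power to detect changes in measures from baseline to the end of the study equivalent to 0.6 standard deviation units", in a paired pre-post framework.

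The causal language is not confined to one sentence. The Aim 2 Expectation presents the hypothesised improvements as the product of training, and the Innovation paragraph promises evidence on functional changes that the intervention brings about.

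**The concern.** A mean change over time in one trained group combines any training effect with everything else that changes between visits: familiarity with the tests, effort by participants who know they are being trained, regression to the mean, and residual recovery or other activity. Attributing the change to training needs something that estimates those other parts. The protocol describes no untrained stroke group and no repeat baseline.

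Some of these explanations arise from the study's own procedures. Dynamometry asks for maximal voluntary effort. Walking speed is measured on a GaitRite mat, and each training session includes 10 fast-walking trials on a GaitRite walkway with real-time speed feedback. Over 24 sessions that is 10 × 24 = 240 trials on the same kind of equipment as the test. Eligibility also depends on treadmill walking at 0.3 to 0.8 m/s, so some regression to the mean on a related outcome is possible.

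What is at stake is the conclusion. Under the present wording, a significant time effect could be read as efficacy, and an unchanged follow-up value as persistence of an effect that training caused.

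**Working it through.** **1. The plan's own figure reproduces.** Inputs, from the sample-size section: "With 28 subjects enrolled and a 15% attrition rate over time (resulting in complete data on 24 subjects"; an effect of 0.6 SD, taken here as SDs of the paired change because the plan uses a paired framework; and "All power estimates assume 2-sided hypothesis tests and an alpha level of 0.05".

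- Completers: 28 × 0.85 = 23.8, about 24.
- Paired t-test power from the noncentral t distribution: df = 24 − 1 = 23; noncentrality = 0.6 × √24 = 2.94. Power = 80.4%, against at least 80% stated.
- Effective sample size with ICC 0.90 and 4 time points: 24 × 4 / (1 + 3 × 0.9) = 96 / 3.7 = 25.9, against about 26 stated. Power at n = 26 is 83.6%, against about 83% stated.

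The arithmetic is sound. It is, however, power to detect any mean change from baseline, whatever the cause.

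**2. What the same test does if training has no effect.** The documents give no estimate of change without training, so the shifts below are assumptions. Same formula, n = 24, with noncentrality = shift × √24:

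| Assumed shift from other causes (SD of change) | Probability of a significant result |
|---|---|
| 0 | 5.0% |
| 0.1 | 7.6% |
| 0.2 | 15.6% |
| 0.3 | 29.1% |
| 0.4 | 46.7% |
| 0.5 | 65.0% |

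**3. Is there a comparator anywhere in Aim 2?**

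- *Healthy controls.* They do not train, and they serve the baseline leg comparison in Aim 1.
- *Non-paretic leg.* It is trained too, so the secondary between-leg analysis compares two treated legs.
- *Model terms.* Time is the key variable; there is no group or group-by-time term.
- *Historical locomotor-training cohort.* It appears only in the Aim 3 secondary questions and had its own active treatment.

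**4. Persistence.** The visit 8 weeks after training can describe whether an observed change is retained. It cannot show persistence of a training-caused effect when that effect has not been isolated. The Aim 2 analysis plan names no specific contrast between week 8 and follow-up. For strength and power there is also a point to reconcile: the Aim 2 summary includes dynamometry at follow-up, while the Dynamometric Assessment section lists only the visits before training and at 4 and 8 weeks.

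**5. Outcomes are not equally exposed.** Muscle cross-sectional area comes from MRI and [Pi] from spectroscopy at rest; practice and effort are unlikely to move either much. Peak torque, peak power and walking measures depend on voluntary performance. The efficacy statement covers all of them without distinction.

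**The case against.** The strongest case on the other side has four parts.

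- *Safeguards exist.* Enrolment at 6 to 24 months after stroke is meant to leave early natural recovery behind. Dynamometry includes familiarisation, warm-up and extra contractions when trials disagree, and treadmill testing allows a practice trial. Clinical assessments use a therapist blinded to training response. These reduce some rival explanations. But late enrolment addresses recovery only, familiarisation works within a session rather than between visits, and the assessor's blinding does not mask participants.
- *The analysis is already framed as change.* The analysis plan and the power statement both speak of changes over time or from baseline. This stands, and it is why no model or sample size needs to alter. The objective and expectation still say more than that analysis can deliver.
- *A single arm is legitimate for a mechanistic study.* Agreed. A reader might infer that a control arm is being demanded. It is not, and the present sample could not support one: if 0.6 SD were the between-arm difference in change, with equal SDs, 12 completers per arm would give about 29% power. A two-arm study would need 45 per arm, or 45 / 0.85 = 53 per arm (106 in total) after 15% attrition.
- *The supplied text may be incomplete.* The walking protocol refers to a limitations section that is not in the text available. Nothing is inferred from its absence; the Aim 2 sentences would need rewording in any case.

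**Conclusion.** The concern holds as a mismatch between claim and design. Aim 2 can show within-patient change during training and whether it is retained 8 weeks later. It cannot determine efficacy, or persistence of an effect caused by training. The problem is greatest for dynamometry and walking measures and smaller for cross-sectional area and resting [Pi].

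Its size cannot be estimated from the documents. The 7.6% to 65.0% range rests on assumed shifts of 0.1 to 0.5 SD, a true training effect of zero, 24 completers and the plan's paired framework. It illustrates the issue and is not a forecast.

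Stronger readings that the documents do not support:

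- *That observed gains will be artefact.* No figure for untrained change is given, so neither its presence nor its size can be asserted.
- *That a share of the 0.20 m/s pilot gain in gait speed can be assigned to drift.* The documents supply no drift figure, the gain comes from five people, and self-selected speed is modelled in Aim 3.
- *That the historical-cohort comparison inherits an efficacy claim.* The Aim 3 secondary questions already call it exploratory, post hoc and not powered for differences in efficacy, and set no hypothesis about them.

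**What to change.** Restate the Aim 2 objective, expectation and planned conclusions as within-patient change during training and retention of that change at the visit 8 weeks after it ends. Carry the same wording into the Innovation paragraph. State beforehand that a significant time effect will not be reported as efficacy or attributed to training alone.

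No model, sample size, visit or added arm is involved. A repeat baseline is not requested, because the documents do not establish that participants attend more than one pre-training test visit. The cost is an edit to the text and a less favourable claim.
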